 # indicates items with recalibrated scores

Computing normalized domain scores

For each of the individual domain the scale 0-100 score is standardized using a z-score transformation. The z score is computed by subtracting the mean 0-100 general US population score (1998) from the computed scale 0-100 score and dividing the difference by the corresponding domain standard deviation from the 1998 general U.S. population as detailed in SF-36 Physical and Mental Health Summary Scales: How to score Version 2 of the SF-36 Health Survey [Ware 2000].

Calculations of the Z scores using 1998 General US population Means and SD are as follows:

$$PF_z = (PF - 83.29094) \div 23.75883$$

$$RP_z = (RP - 82.50964) \div 25.52028$$

$$BP_z = (BP - 71.32527) \div 23.66224$$

$$GH_z = (GH - 70.84570) \div 20.97821$$

$$VT_z = (VT - 58.31411) \div 20.01923$$

$$SF_z = (SF - 84.30250) \div 22.91921$$

$$RE_z = (RE - 87.39733) \div 21.43778$$

$$MH_z = (MH - 74.98685) \div 17.75604$$

Each of the individual domain z-score is then transformed to norm based (mean 50, standard deviation 10) scoring (also known as t scores) by multiplying each domain z-score by 10 and adding the resulting product to 50.

Normative domain scores:

$$PF_t = (PF_Z \times 10) + 50$$

$$RP_t = (RP_Z \times 10) + 50$$

$$BP_t = (BP_Z \times 10) + 50$$

$$GH_t = (GH_Z \times 10) + 50$$

$$VT_t = (VT_Z \times 10) + 50$$

$$SF_t = (SF_Z \times 10) + 50$$

$$RE_t = (RE_Z \times 10) + 50$$

$$MH_t = (MH_Z \times 10) + 50$$

Computing PCS and MCS measures

Physical and Mental Component Summary measures (PCS and MCS respectively) are also calculated. These are aggregate scores for the physical and mental components which are computed by multiplying each of the individual domain z-scores (calculated as described above) by their respective physical/mental factor score coefficients and summing the eight products.

Aggregate component summaries are derived as follows:

$$PCS_Z = (PF_Z \times 0.42402) + (RP_Z \times 0.35119) + (BP_Z \times 0.31754) + (GH_Z \times 0.24954) + (VT_Z \times 0.02877) + (SF_Z \times -0.00753) + (RE_Z \times -0.19206) + (MH_Z \times -0.22069)$$

$$MCS_Z = (PF_Z \times -0.22999) + (RP_Z \times -0.12329) + (BP_Z \times -0.09731) + (GH_Z \times -0.01571) + (VT_Z \times 0.23534) + (SF_Z \times 0.26876) + (RE_Z \times 0.43407) + (MH_Z \times 0.48581)$$

Each summary measure is then transformed to the norm-based (mean 50, standard deviation 10) scoring (t scores). This is accomplished by multiplying each aggregated score by 10 and adding the resulting product to 50.

$$\text{Normative Physical Component Summary score: } PCS_t = (PCS_Z \times 10) + 50$$

$$\text{Normative Mental Component Summary score: } MCS_t = (MCS_Z \times 10) + 50$$

Handling of Missing data

Imputation for missing items in a domain

For an individual domain where 50% or more of the item questions are non-missing, the average of the non-missing items for that patient in that domain is calculated. This

average is then be used to impute the remaining missing item questions of that domain. Note: imputation should be based on the final domain score after recalibration / reverse scores of pre coded scores.

However, if more than 50% of item questions are missing the domain is recorded as missing.

Aggregated scores are computed after the imputation rule has been applied to the component domains, but are set to missing if any domain is missing.

Handling of duplicate entries on Questionnaire form

Duplicate entries within the same day for a question item are handled as follows:

- If a respondent marks two responses which are adjacent to each other, then the worst case (lowest value) is selected. Note this is selected based on the item score after recalibration / reverse scores of pre coded scores.
- If a respondent marks two responses which are not adjacent to each other, then the score is missing for that item
- If a respondent marks three or more responses then the score is missing for that item

C.5. WPAI:MS scoring

The four WPAI:MS outcome scores are defined based on the outcome Q1–Q6 of Questions 1–6 (ref: http://www.reillyassociates.net/WPAI_Scoring.html):

Q1 = currently employed (Y/N)

Q2 = hours missed due to MS

Q3 = hours missed other reasons

Q4 = hours actually worked

Q5 = degree MS affected productivity while working

Q6 = degree MS affected regular activities

WPAI:MS outcome scores are defined as detailed below. At each assessment visit for those who are currently employed the following 3 scores are defined:

- **Absenteeism:** Percent work time missed due to MS = $Q2 / (Q2 + Q4) \times 100$
- **Presenteeism:** Percent impairment while working due to MS = $Q5 / 10 \times 100$
- **Work productivity loss:** Percent overall work impairment due to MMS = $\{Q2 / (Q2 + Q4) + [(1-Q2 / (Q2 + Q4)) \times (Q5 / 10)]\} \times 100$

For all subjects irrespective of their current employment status

- **Activity impairment:** Percent activity impairment due to MS = $Q6 / 10 \times 100$

Scoring: Handling of missing or inconsistent data

The following rules for handling of missing or inconsistent data within the same day are implemented as described in the section “Coding Rules for Self-Administration” by Reilly Associates [Reilly Associates 2002].

- *Employment status (Q1):*

If Q1 = ‘YES’ or Q1 = ‘NO’ or ‘missing’ and hours missed (Q2) or hours worked (Q4) > 0, then subjects is considered employed.

If Q1 = ‘missing’ and hours missed (Q2) and hours worked (Q4) = 0, then considered not employed (i.e., Q1 considered No).

- *Hours missed (Q2) and hours worked (Q4)*

If hours worked (Q4) = 0, then productivity while at work (Q5) is not applicable and considered as missing.

If subject enters a range of hours for (Q2 or Q4), use the midpoint.

If a subject is considered employed but hours missed (Q2) is missing, then impute as zero.

- *Productivity Questions (Q5 and Q6)*

If for one question, two responses are provided, enter the midpoint and round to nearest integer.

Missing response after applying the above scoring

WPAI scores cannot be calculated if there is a missing response to one or more corresponding individual questions.

D. Laboratory marked abnormalities

Table 13 **Thresholds for marked laboratory abnormalities**

Parameter (SI unit)	LL	LLL	HH	HHH
Hemoglobin (g/L)	< 100	< 80	> 20 g/L above ULN (for pre-treatment assessments, and post-treatment assessments when baseline \leq ULN) or increase from baseline > 20 g/L (for post-treatment assessments when baseline is > ULN)	> 40 g/L above ULN (for pre-treatment assessments, and post-treatment assessments when baseline \leq ULN) or increase from baseline > 40 g/L (for post-treatment assessments when baseline is > ULN)
Hematocrit (L/L)	< 0.28 (female) < 0.32 (male)	< 0.20	> 0.55 (female) > 0.60 (male)	> 0.65
Platelet count (10^9 /L)	< 75	< 50	> 600	> 999
WBC count (10^9 /L)	NA	< 1.9	> 20.0	> 100.0
Lymphocyte (10^9 /L)	ND	< 0.2	> 4.0	> 8.0
Neutrophils (10^9 /L)	< 1.5	< 1.0	ND	ND
Eosinophils (10^9 /L)	ND	ND	> 5.0	ND
Polymorphonuclear leucocyte/Band cells (%)	ND	ND	> 90%	> 95%
AST (U/L)*	ND	ND	≥ 3 ULN	≥ 5 ULN
ALT (U/L)*	ND	ND	≥ 3 ULN	≥ 5 ULN
Total bilirubin (umol/L)	ND	ND	≥ 2 ULN	≥ 5 ULN
Alkaline Phosphatase (U/L)	ND	ND	> 2.5 ULN	> 5 ULN
INR*	ND	ND	> 1.5 ULN	> 2.5 ULN
Creatinine (umol/L)*	ND	ND	>1.5 ULN or >1.5 \times baseline	> 3 ULN or >3 \times baseline
Creatinine clearance (mL/min)	< 60	< 30	ND	ND
Urea (mmol/L)	ND	ND	> 2.5 ULN	> 5 ULN
Albumin (g/L)	< 30	< 20	ND	ND
Glucose (mmol/L)	< 3.0	< 2.2	> 8.9	>13.9
Potassium (mmol/L)	< 3.2	< 3.0	> 5.5	> 6.0
Sodium (mmol/L)	ND	< 130	> 150	> 155
Calcium (mmol/L)	< 2.0	< 1.75	> 2.9	> 3.1
Triglyceride (mmol/L)	ND	ND	> 3.42	> 11.4
Cholesterol (mmol/L)	ND	ND	> 7.75	> 12.92

* HH and HHH based on CTCAE 2010 v4.03. ALT = alanine aminotransferase; AST = aspartate aminotransferase; ND = not defined; may be complemented by definitions provided by the central laboratory (see central laboratory manual); ULN = upper limit of normal.
 Source: Protocol AC-058B301, appendix 6.

E. Document history

Version	Effective Date	Reason (main)
1.0	11 Dec 2018	New
2.0	20 June 2019	
FSIQ-RMS responder threshold added based on results from anchor analysis
 
Minor update for efficacy analyses: estimates per treatment arm (least square means) derived based on observed margins
 
12-week and 24-week CDA: handling of relapse start date and end date clarified; alternative censoring approach added based on health authority feedback.
 
Safety analyses: Additional analyses added, small updates based on health authority feedback including presentation of AEs from Day 1 to Day 16 and updates to blood pressure and heart rate abnormality thresholds.
 
Editorial updates have been applied.

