5.7 Pharmacoeconomic variables

5.7.1 Change from baseline by visit up to Week 108 in Work productivity and activity impairment (WPAI:MS) scores

The WPAI:MS V2.0 assesses work productivity and activity impairment. It has a recall period of 7 days. The following variables are considered:

- **Current paid employment status (Y/N)**

Four WPAI:MS outcome scores are considered that are expressed as impairment percentages, with higher numbers indicating greater impairment and less productivity:

- Percentage of work time missed due to MS (absenteeism),
- Percentage of impairment while working due to MS (presenteeism),
- Percentage of overall work impairment due to MS,
- Percentage of activity impairment due to MS.

The first three of these outcomes will be calculated only for those subjects who are working for pay, and the last outcome will be calculated for all subjects. See Appendix C.5 for details on the scoring.

WPAI is completed by the subject on an electronic device at Visit 2 (Baseline), and at Visits 6, 7, 10, and 12 (Weeks 12, 24, 60, 84, respectively), 14 (Week 108). For analysis, visits are assigned based on time windowing, as detailed in Section 11.3.

Absolute change from baseline is derived with baseline defined as last available score up to and including randomization date.

5.7.2 Health care resource utilization from baseline up to Week 108

Health care resource utilization data is taken from the following CRF pages: Hospitalization as recorded on the Adverse events, and 'Relapse summary' forms. Intensive care unit admissions for MS relapses are taken from 'Intensive Care Unit Admissions for MS Relapses' form. Emergency room visits for MS are taken from the 'Emergency medical facility visits for MS' form.

The following health care resource utilization variables will be derived:

- Number of admissions / visits from baseline to Week 108 (Frequency of health care resource utilizations)
- Length of stay (days) from baseline to Week 108 (Duration of health care resource utilizations)

The variables above are derived for the following categories

- Any hospitalization: Derived from the Adverse event, Relapse summary and ‘Intensive Care Unit Admissions for MS Relapses eCRFs.
- Hospitalizations due to AEs: Derived from the AE page
- Hospitalizations due to relapses: Derived from the Relapse summary eCRF

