9.12 Analysis of pharmacoeconomic variables

9.12.1 Change from baseline by visit up to Week 108 in WPAI:MS scores

Analyses will be summarized and listed on the FAS. WPAI scores and number of subjects currently employed by visit during the main study are summarized per treatment group. WPAI-MS outcome measures (absenteeism, presenteeism, overall work impairment and activity impairment) will be graphically presented over time using mean \pm SE.

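### Appendix C.5 makes overall work impairment missing for employed subjects who worked no hours and missed some because of MS, although the SAP's own formula gives 100%

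*SAP*

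**What the plan says.** SAP Section 5.7.1 lists four WPAI:MS scores, "with higher numbers indicating greater impairment and less productivity". Three of them, including overall work impairment, apply only to subjects in paid work. Section 9.12.1 summarizes the scores by treatment group on the FAS and adds a plot: "WPAI-MS outcome measures (absenteeism, presenteeism, overall work impairment and activity impairment) will be graphically presented over time using mean" ± SE.

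Appendix C.5 gives the formulas:

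- Absenteeism, "Percent work time missed due to MS": Q2/(Q2+Q4) × 100.
- Presenteeism: Q5/10 × 100.
- Work productivity loss, "Percent overall work impairment due to MMS" (the last word is evidently a typing error for MS): {Q2/(Q2+Q4) + [(1 − Q2/(Q2+Q4)) × (Q5/10)]} × 100.

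The rules for missing or inconsistent data follow. On employment, whatever the answer to Q1: "hours missed (Q2) or hours worked (Q4) > 0, then subjects is considered employed". On hours worked: "If hours worked (Q4) = 0, then productivity while at work (Q5) is not applicable and considered as missing". Last, under the line "Missing response after applying the above scoring", comes: "WPAI scores cannot be calculated if there is a missing response to one or more corresponding individual questions". No exception is made for zero hours worked, and no imputation is given for Q5.

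**The concern.** Setting Q5 to missing when no hours were worked is sensible for presenteeism, because impairment while working has no meaning for someone who did not work. The same step also removes the overall score, which in this situation does not depend on Q5.

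The excluded value is always 100%, the top of the scale. Leaving it out can only lower the visit mean, unless everyone else also scores 100%. If the affected fraction differs between arms, the descriptive comparison is distorted as well. A subject whose score would have risen to 100% instead has no change from baseline at that visit. Section 5.7.1 defines no LOCF version for WPAI:MS, unlike Section 5.6.1 for SF-36, so nothing puts these subjects back.

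**Working it through.** The SAP states no numerical result on this point, so there is no figure to reproduce. The check evaluates the C.5 formulas and then applies the C.5 missing-data rules in the order given.

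**1. The affected subject.** Q2 > 0 and Q4 = 0. By the employment rule the subject counts as employed, so the overall score is meant to exist.

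**2. Formula.** Q2/(Q2+Q4) = Q2/Q2 = 1, so the weight on Q5 is 1 − 1 = 0. Overall impairment = {1 + 0 × Q5/10} × 100 = 100%. Evaluating it for Q2 = 8, 20 and 40 hours with every Q5 from 0 to 10 gives 100% each time.

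**3. Rules.** Q4 = 0 sets Q5 to missing. Q5 is a component of the overall score, so the final rule makes that score missing.

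**4. Same subject, other scores.**

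| Score | Questions used | Result under C.5 |
|---|---|---|
| Absenteeism | Q2, Q4 | 100% |
| Presenteeism | Q5 | missing (rightly) |
| Overall work impairment | Q2, Q4, Q5 | missing; the formula gives 100% |
| Activity impairment | Q6 | scored from Q6 |

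**5. A near neighbour.** With Q2 = 39 and Q4 = 1, Q2/(Q2+Q4) = 0.975. Overall impairment is (0.975 + 0.025 × 0) × 100 = 97.5% at Q5 = 0 and (0.975 + 0.025 × 1) × 100 = 100% at Q5 = 10. This subject stays in the summary. The score approaches 100% as hours worked fall to zero and then becomes missing at zero.

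**6. Effect on the mean.** Let f be the fraction of subjects affected at a visit, among those whose overall score the formula determines, and m the mean of the others. The mean by formula is (1 − f) × m + f × 100. The reported mean is m. The understatement is the difference, f × (100 − m).

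The SAP gives no values for f or m, so the following are assumptions:

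| f | m | Mean by formula | Reported mean | Understatement (points) |
|---|---|---|---|---|
| 1% | 25% | 25.75% | 25% | 0.75 |
| 3% | 25% | 27.25% | 25% | 2.25 |
| 5% | 25% | 28.75% | 25% | 3.75 |

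Over the wider assumed ranges m = 20% to 30% and f = 1% to 10%, the understatement runs from 0.01 × (100 − 30) = 0.7 to 0.10 × (100 − 20) = 8.0 points.

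**The case against.** Several objections limit the point.

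- **Only one score of four is wrongly lost.** A reader might infer that the worst-affected subjects disappear from the WPAI:MS results altogether. They do not: absenteeism is kept at 100%, activity impairment is scored from Q6, and presenteeism is properly not applicable. Because absenteeism is reported for the same arm and visit, the absence remains visible there. This stands.
- **Zero hours worked is not always a full week lost to MS.** Q3, hours missed for other reasons, is not in the formula. A subject with Q2 = 2, Q3 = 38 and Q4 = 0 also scores 100%. So the affected group should not be read as people off work all week because of MS. This stands, but it is a property of the SAP's formula, and absenteeism already gives that subject 100%.
- **Missingness has other causes.** The overall score is also missing when Q4 is missing, when Q5 is unanswered with Q4 > 0, and when Q2 = Q4 = 0 (0/0). It would be wrong to say that the worst outcome alone determines missingness.
- **Bias at every visit is not shown.** WPAI:MS is scheduled only at Baseline and Weeks 12, 24, 60, 84 and 108, with a 7-day recall. Section 5.7.1 lists no relapse-visit assessment, so an absence from relapse counts only if it falls in one of those recall weeks. Understatement arises only at visits with an affected subject.
- **The size rests on assumption.** This applies equally to any difference between arms. With 5% affected in one arm, 2% in the other and m = 25% in both, 0.05 × 75 − 0.02 × 75 = 2.25 points would vanish, but the split is assumed. The documents do not show that a real benefit or harm is hidden.
- **The rules are credited to published coding rules that are not at hand.** Whether that source treats this case separately cannot be checked here. The credit explains where the rules came from; it does not remove the conflict with the formula in the same appendix.

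**Conclusion.** The point holds for one score. For an employed subject with Q2 > 0 and Q4 = 0, the C.5 formula fixes overall work impairment at 100%, and the missing-data rules in the same appendix make it missing. That part needs no assumption. At visits where such subjects occur, the mean is understated by f × (100 − m): 0.75 to 3.75 points for assumed f = 1% to 5% and m = 25%, with no SAP data to narrow the range.

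WPAI:MS is a descriptive pharmacoeconomic outcome outside the testing strategy of Section 9.1.1, so no tested endpoint changes. The correction is still worth making before analysis, because the rule as written discards a determinate value, always at the worst end of the scale.

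**What to change.** Add one sentence to Appendix C.5, after the rule on Q4 = 0: if the subject is considered employed, Q2 > 0 and Q4 = 0, overall work impairment is set to 100%, as the formula gives, and presenteeism remains missing.

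Leave all other missing-data rules unchanged. Q4 missing, Q5 missing with Q4 > 0, and Q2 = Q4 = 0 (including Q2 imputed as zero) still give missing values for the scores that need them. The new sentence should not be worded so that it overrides these.

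Add a note that Q3 is not in the formula. The 100% then means that all hours counted by the formula, worked or missed because of MS, were lost, which is consistent with the absenteeism score.

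The cost is the SAP text and one line of code, with no new data. The sponsor should also compare the sentence with the cited coding rules and record any departure, so that comparability with other uses of the instrument is clear.
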